### 5.2 Safety Population

The Safety Population will include all subjects receiving at least one dose of study treatment. The subjects will be grouped according to the highest treatment regimen actually reached.. Anyone with mean total daily dose  $> 0$  and  $\leq 100$  mg BID will be included in the 100 mg BID group, anyone with mean total daily dose  $> 100$  mg BID will be included in the 150 mg BID group. The Safety Population will be used for the safety analyses.

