7.9.4 Safety Analyses

The safety analysis will be conducted on the safety set. The AEs will be coded according to the MedDRA and treatment-emergent adverse events (TEAEs) summarized by treatment group, system organ class and preferred term. Further summaries will be done by seriousness, severity, relationship to study treatment and actual dose at the time of onset.

Vital signs, ECG data and laboratory tests at baseline (last non-missing results prior to the first dose of study drug, each postbaseline visit, and changes from baseline to each of the postbaseline visits will be summarized with descriptive statistics. Shift tables for the laboratory tests based on a classification of values as low, normal, or high with respect to the reference range will be summarized.

For vital signs, orthostatic hypotension is defined as a reduction of 20 mmHg or more in systolic blood pressure, or a reduction of 10 mmHg or more in diastolic blood pressure, for the standing measurement compared to the supine measurement. The proportion of patients with orthostatic hypotension will be summarized with shift tables.

Prilenia Therapeutics

Protocol: PL101-LID201 Protocol Amendment 1/v2.0

Pridopidine

19 Nov 2019

For ECG data, absolute QTcF of >450 msec, >480 msec, and >500 msec, changes from baseline in QTcF>30 msec and <60 msec, and changes in QTcF>60 msec throughout the study will be summarized.

All other safety data will be summarized with descriptive methods.

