## 4.2 Study Treatment

Subjects who met eligibility criteria were randomly assigned at Baseline (Visit 2) to receive pridopidine 100 mg BID, 150 mg BID or placebo using a 1:1:1 randomization. No stratification factors were used in the randomization. During the 14/16-week active treatment period, two oral capsules were taken in the morning (at 7:00 AM  $\pm$ 1 hour) and 2 oral capsules in the afternoon (at 1:00 PM  $\pm$ 1 hour). The time difference between the 2 administrations was 6-8 hours apart.

Subjects in the active treatment arms underwent either a 2-week (original amendment) or a 4-week (Amendment 1) dosage titration period as described below:

- Original protocol: Subjects who underwent a 2-week titration period were treated for 3 days with pridopidine 75 mg QD (once daily), 4 days of pridopidine 75 mg BID, and 1 week with pridopidine 100 mg BID.
- Amendment 1: Subjects who underwent a 4-week titration period were treated with pridopidine 75 mg on alternate days (Q48h) during one week, 75 mg QD during 1 week, 75 mg BID during 1 week, and 100 mg BID during one week.

Under both protocol versions, maintenance treatment with pridopidine 100 mg BID or 150 mg BID was then continued for an additional 12 weeks.

Subjects randomly assigned to the placebo arm received matching placebo throughout the treatment period in a double-blind fashion at the same dosing schedule as subjects assigned to the active treatments.

At the end of the maintenance period or at early termination (ET), all subjects underwent a down-titration period in which they received 1 capsule of pridopidine 75 mg (or the matching placebo) and 1 capsule of

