## 5 Analysis Populations

The following analysis populations (analysis sets) will be used for the analysis of the disposition, demographic, efficacy, safety and PK data.

Subjects will be grouped according to the actual treatment received if there were inaccuracies in study drug taken compared to what treatment subjects were randomized to.

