### 5.1 Efficacy Evaluable (EE) Population

The Efficacy Evaluable 1 (EE1) population includes all subjects that were randomized, received at least 80% of their dose of study drug and were on treatment at Visit 3 (Week 3/5) and have a post-randomization assessment of the primary endpoint.

The Efficacy Evaluable 2 (EE2) population includes all subjects who were on treatment at Visit 5 (Week 8/10), have at least 80% compliance to study drug and have a valid assessment of the primary endpoint.

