### 15.2 Compliance

Subjects will be instructed to bring with them the used and unused drug kits at Visit 3, Visit 5, Visit 6, Visit 7/ET, and at Visit 8/FU, in which treatment compliance will be evaluated. Treatment compliance at the Visit 3, Visit 5, Visit 6, Visit 7/ET, and Visit 8/FU and overall for the 14 week active treatment period will be calculated using the following formula:

$$\text{Compliance (\%)} = [\text{Total number of administered doses} / \text{Total number of scheduled doses}] \times 100$$

The total number of scheduled doses will be calculated based on the extent (days) of exposure of each subject. A range between 80% to 120% will be taken as reference limits for a satisfactory level of compliance. The compliance (expressed as %) will be summarized with descriptive statistics by treatment group. In addition, the number (and %) of subjects with compliance between 80% to 120% will be tabulated by treatment group.

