## Statistical Analysis Plan

In the AE summaries, data will be presented in four columns (pridopidine 150 mg BID, pridopidine 100 mg BID, pridopidine total, placebo) using the Safety Population.

The following summaries will be provided. If not stated otherwise, the tables will be sorted in alphabetic order by SOC, and within each SOC, in descending order according to the % of subjects reporting each PT in the pridopidine total group.

- An overall summary of the number and percentage of subjects reporting TEAEs and the number of TEAE events, treatment-related TEAEs, severe TEAEs, TEAEs leading to death (if there are any subjects who died), SAEs other than death, TEAEs leading to study drug discontinuation and TEAEs leading to temporary withdrawal
- The incidence (number and % of subjects) and frequency (event count) of TEAEs broken down by System Organ Class (SOC) and PT.

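### SAP 5.2 sets two conflicting rules for the by-dose safety columns, and one can move early stoppers on 150 mg BID into the 100 mg BID column

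*SAP*

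**What the plan says.** SAP 5.2 gives two allocation rules in consecutive sentences:

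- Highest regimen: "The subjects will be grouped according to the highest treatment regimen actually reached".
- Mean dose: a patient whose mean total daily dose is above zero and at most 100 "mg BID will be included in the 100 mg BID group, anyone with mean total daily dose" above 100 mg BID is placed in the 150 mg BID group.

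No order of precedence is given. The mean has no stated averaging period, does not say whether titration and down-titration count, and does not say whether doses are scheduled or taken. A total daily dose is also expressed in mg BID.

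The opening of SAP Section 5 adds a general rule: "Subjects will be grouped according to the actual treatment received if there were inaccuracies in study drug taken". It covers patients whose drug differed from their randomised treatment and does not choose between the two sentences.

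SAP 15.3 builds the adverse-event tables on this grouping: "data will be presented in four columns (pridopidine 150 mg BID, pridopidine 100 mg BID, pridopidine total, placebo) using the Safety Population". The laboratory and ECG summaries in SAP 15.4 and 15.6 are also by treatment group. Protocol 7.9.4 planned a further adverse-event table: "Further summaries will be done by seriousness, severity, relationship to study treatment and actual dose at the time of onset". The summaries listed in SAP 15.3 do not include one by dose at onset.

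**The concern.** The highest regimen reached and the mean daily dose are different statistics. Both active arms titrate identically and stay at or below 200 mg/day until maintenance begins. SAP 4.2 confirms that two schedules are pooled: "Subjects in the active treatment arms underwent either a 2-week (original amendment) or a 4-week (Amendment 1) dosage titration period as described below". A mean that includes those weeks stays below the current dose for some time after a patient moves to 150 mg BID.

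A patient who reaches 150 mg BID and stops soon afterwards is therefore in the 150 mg BID column under the first sentence and may be in the 100 mg BID column under the second. All of that patient's adverse-event, QTcF and creatinine data move too. At prescribed doses the shift runs one way, from high dose to low, and it concerns early stoppers, where dose-related intolerance would be expected to show. Protocol 1.2.1.1 gives 112.5 mg BID as the highest dose previously tested in humans, so 150 mg BID is the column where clean attribution matters most. SAP 9.3 says the study ended before 30 subjects were enrolled, so each column is small.

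**Working it through.** The SAP gives no figure of its own here. The check is how long a patient can take 150 mg BID before a mean-dose rule recognises it.

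**Inputs**

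- 100 mg BID is 200 mg/day and 150 mg BID is 300 mg/day (Protocol synopsis). The cut is taken as 200 mg/day.
- Four-week titration (SAP 4.2), with the alternate-day week assumed to hold 4 doses: 4×75 + 7×75 + 7×150 + 7×200 = 3275 mg over 28 days, mean 117.0 mg/day.
- Two-week titration (SAP 4.2): 3×75 + 4×150 + 7×200 = 2225 mg over 14 days, mean 158.9 mg/day.
- Down-titration: 2×150 + 2×75 = 450 mg over 4 days.
- Maintenance: 12 weeks, 84 days.

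**Formula.** With m days at 300 mg/day, the patient is labelled 100 mg BID while (titration mg + 300m) / (titration days + m) ≤ 200.

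- Calendar days, full dosing, four-week: 3275 + 300m ≤ 5600 + 200m, so m ≤ 23.25, or 23 days. The mean is 199.5 on Day 51 and 201.4 on Day 52.
- Same, two-week: 2225 + 300m ≤ 2800 + 200m, so m ≤ 5.75, or 5 days.
- Down-titration counted: 3725 + 300m ≤ 200(32 + m) gives 26 days; 2675 + 300m ≤ 200(18 + m) gives 9 days.
- Dosing days only, four-week: 3275 + 300m ≤ 200(25 + m) gives 17 days. The two-week schedule doses every day, so it stays at 5.
- Doses taken at 90%: 0.9(3275 + 300m) ≤ 200(28 + m) gives 37 days; 0.9(2225 + 300m) ≤ 200(14 + m) gives 11 days.
- Doses taken at 80%: 0.8(3275 + 300m) ≤ 200(28 + m) gives 74 days; 0.8(2225 + 300m) ≤ 200(14 + m) gives 25 days.

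| Reading of the mean | Four-week titration | Two-week titration |
|---|---|---|
| Maintenance only, full dosing | 0 days | 0 days |
| Dosing days only | 17 | 5 |
| Calendar days, full dosing | 23 | 5 |
| Calendar days plus down-titration | 26 | 9 |
| Doses taken, 90% compliance | 37 | 11 |
| Doses taken, 80% compliance | 74 | 25 |

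The 80% row uses the SAP's own lower limit (SAP 15.2): "A range between 80% to 120% will be taken as reference limits for a satisfactory level of compliance". It also meets the EE2 criterion in SAP 5.1, under which patients must "have at least 80% compliance to study drug and have a valid assessment of the primary endpoint". At Visit 5 on the four-week schedule (Day 70, m = 42) the scheduled mean is (3275 + 12600)/70 = 226.8 mg/day, and 80% of that is 181.4. Such a patient is labelled 100 mg BID for safety while satisfying the EE2 compliance limit.

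**Reverse shift, if doses taken are used.** A 100 mg BID completer on the two-week schedule has a scheduled mean of (2225 + 84×200)/98 = 194.1 mg/day. The cut is passed at 200/194.1 = 103.0% of doses. Counting down-titration, the threshold is 102×200/19475 = 104.7%. On the four-week schedule without down-titration the mean is (3275 + 16800)/112 = 179.2 and the threshold is 111.6%. All three lie inside the 80–120% range.

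**Who is not affected.** Fully dosed 12-week completers on 150 mg BID average 254.2 (four-week) or 279.8 mg/day (two-week) and are classed correctly.

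**The case against.** The best counter-reading is that the second sentence merely applies the first. It gives a column to patients who never reached 100 mg BID, whom the first sentence leaves without one, and its cut is written in regimen notation. If the mean covers maintenance only, the two rules agree at prescribed doses. But the SAP does not restrict the mean in that way. That restriction would also leave the mean undefined for patients who stop in titration, the group the sentence is said to serve.

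Several narrower points do stand:

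- The 37- and 74-day figures need doses taken rather than prescribed, uniform under-dosing from Day 1, and titration included. They show the upper range, not the expected case.
- The 103.0% reverse threshold is the lowest of the three shown and needs over-consumption sustained throughout treatment.
- The Section 5 sentence is a misallocation rule and does not compete for the dose columns.
- SAP Appendix 21.1, the list of tables, is not in the text available, so a dose-at-onset table could be there. What can be said is that SAP 15.3 does not list one.
- Subject listings remain, and in a study this small a reader could check events against dose by hand. That mitigates the error in the tables without removing it.

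**Conclusion.** The concern holds. SAP 5.2 contains two rules that can place the same patient in different safety columns, and nothing in the SAP settles which applies. At full prescribed dosing, patients stopping within the first 23 maintenance days (four-week titration) or 5 days (two-week) are misplaced if the mean runs over calendar days from first dose. The range across readings is 0 to 74 days and 0 to 25 days respectively.

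These limits assume a 200 mg/day cut, four doses in the alternate-day week and no dose reductions. Counting the first maintenance day as 250 mg, or allowing one three-day reduction, moves the calendar-day limits, with or without down-titration, by 0 to 5 days.

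The number of patients who stopped inside these windows, and the split between titration schedules, are not in the documents, so the effect on any table cannot be stated. The placebo and pridopidine total columns and the underlying listed data do not change.

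**What to change.** SAP Section 2 says the plan is being finalised before database lock and unblinding, so the rule can still be settled without knowledge of the results:

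1. Delete the mean-dose sentence from SAP 5.2. Keep the highest-regimen rule and make it explicit: any dose taken at 150 mg BID places the patient in the 150 mg BID column, and all other active patients go in the 100 mg BID column. The one-dose threshold and the placement of patients who never reached 100 mg BID are clarifications that the present text lacks.
2. Footnote patients randomised to 150 mg BID who stopped during titration.
3. Add to SAP 15.3 the protocol's summary of treatment-emergent adverse events by actual dose at onset, or confirm that Appendix 21.1 already includes it.

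The cost is a short rewording, one footnote and one table, with no new data. The trade-off is that titration-phase events, at or below 200 mg/day, in patients who later reached 150 mg BID will sit in the 150 mg BID column. The dose-at-onset table is needed beside it for that reason. Restricting the mean to maintenance would also remove most of the ambiguity, but it would need a separate rule for patients who stop in titration.

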### 5.3 PK Population

The PK Population will include all subjects in the safety population with at least one pridopidine concentration sample result reported. The PK population will be used for the PK analyses. The PK analyses may or may not be performed based on outcome of other analyses and availability of PK data.

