- y. Investigators must complete a detailed case note at Visit 2 to document the patient’s condition before starting study drug. This will be the baseline in which to compare changes in the patients’ global condition after receiving study drug for rating the CGI-C.
- z. During the 16-week active treatment period, the first study treatment daily dose will be taken between 6:00 and 8:00 AM and the second study treatment daily dose will be taken 6 to 10 hours after the first study treatment dose administration and not later than 5:00 PM. The second study treatment daily dose should be taken 0 to 120 minutes BEFORE the “scheduled levodopa dose” (NOT after). As much as possible, study treatment should be taken at the same

time throughout the study. Capsules will be swallowed whole with water. Study treatment can be taken irrespective of meals. If a patient misses the morning study treatment dose on an in-clinic day, the visit should be rescheduled.

- aa. Study treatment kit for down-titration purposes. At the end of the maintenance period or at ET, active treatment patients will undergo a down-titration period in which they will receive one capsule of pridopidine 75 mg and one capsule of placebo BID on Days 1 to 2 followed by one capsule of pridopidine 75 mg and one capsule of placebo QD on Days 3 to 4 of Week 15. Patients receiving placebo will receive matching placebo at the same dosing schedule as patients assigned to the active treatments.
- bb. Pharmacokinetic sampling will be performed at Visit 4, Visit 6, and Visit 7/ET approximately 1 hour before and 1 to 2 hours after the PM study treatment dose. When concomitant with ECG recording, PK samples will be collected within 30 minutes after the ECG recording. The timing of UDysRS and UDPRS should be prioritized before PK sampling.
- cc. Sampling analyses for DNA extraction will be performed only once during the study at the Screening (Visit 1) or at Baseline (Visit 2).
- dd. Sampling analyses will be performed at Screening (Visit 1) or Visit 2, Visit 5, and Visit 7/ET.
- ee. If a patient misses the morning study treatment dose on an in-clinic day, the visit should be rescheduled.

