## Statistical Analysis Plan

2. To explore the relationship between pridopidine exposure and dyskinesia

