## 6.1 Primary Endpoint: Sum of Parts 1, 3, and 4 of UDysRS

The primary endpoint is the mean change and % change from Baseline (Visit 2) to Week 3/5 (Visit 3) and Week 8/10 (Visit 5) in the sum of Parts 1, 3, and 4 of the Unified Dyskinesia Rating Scale (UDysRS) while the patient is in the peak “ON” state and experiencing maximal peak dose dyskinesia.

The sum of Parts 1, 3, and 4 of the UDysRS will be calculated as the sum of Part 1 (historical disability of ON-dyskinesia impact), Part 3 (objective impairment) and Part 4 (objective disability). The sum scores will be calculated as follows:

- Part 1: sum of UDysRS items 1-11; 0-44 points
- Part 3: sum of UDysRS items 16-22; 0-28 points
- Part 4: sum of UDysRS items 23-26; 0-16 points.

For the sum scores of Parts 1, 3 and 4, the following imputation rules will be used in case of incomplete data:

- Part 1: Part 1 is sum of Part 1A (item 1) and Part 1B (items 2-11)
  - If Part 1A (item 1) is missing, the Part 1 sum score will be set as missing.
  - If there is one missing item in Part 1B (items 2-11), the missing item will be replaced by the average of the non-missing items 2-11 from the same subject.
  - If there is more than one missing item in Part 1B (items 2-11), the Part 1 sum score will be set as missing.
- Part 3:
  - If there is one missing item in Part 3 (items 16-22), the missing item will be replaced by the average of the non-missing items 16-22 from the same subject.
  - If there is more than one missing item in Part 3 (items 16-22), the Part 3 sum score will be set as missing.
- Part 4:
  - If there is one missing item in Part 4 (items 23-26), the missing item will be replaced by the average of the non-missing items 23-26 from the same subject.
  - If there is more than one missing item in Part 4 (items 23-26), the Part 4 sum score will be set as missing.
- Sum of Parts 1, 3 and 4:
  - The sum of Parts 1, 3 and 4 will be calculated only if sum of Part 1, sum of Part 3 and sum of Part 4 are all non-missing, after applying the imputation rules presented above. Otherwise, the sum of Parts 1, 3 and 4 will be set as missing.

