## 16 Analysis of PK

Plasma concentrations of pridopidine and its metabolite TV-45065 will be summarized with descriptive statistics by visit and timepoint (1 hour before and 1 to 2 hours after the pridopidine dose). The relationship between plasma concentrations of pridopidine and TV-45065 versus the primary endpoint (and the change from baseline in the primary endpoint) may be explored graphically for each visit which include both the PK and primary efficacy assessments. Separate exploration may be conducted for the PK assessments conducted before and 1 to 2 hours after the pridopidine dose.

PK analyses will be performed after the study database is locked, the study unblinded only if they are deemed necessary. Otherwise, PK data will only be included in listings, if there is not much data for analysis.

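### The SAP lets the outcome of other analyses decide, after unblinding, whether the PK analyses are run, although they serve two stated objectives

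*SAP*

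**What the plan says.** SAP Section 3.4 carries over both PK objectives from the protocol: to describe the PK of pridopidine and its metabolite TV-45065, and "To explore the relationship between pridopidine exposure and dyskinesia".

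Two later SAP sections make the analyses behind those objectives optional. Section 5.3 states: "The PK analyses may or may not be performed based on outcome of other analyses and availability of PK data". Section 16 states: "PK analyses will be performed after the study database is locked, the study unblinded only if they are deemed necessary", and continues: "Otherwise, PK data will only be included in listings, if there is not much data for analysis". The exposure plot is optional a second time within Section 16: concentrations against the primary endpoint, and against its change from baseline, "may be explored graphically for each visit which include both the PK and primary efficacy assessments".

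Protocol Section 7.9.3 has no such condition. It commits to the PK analysis and to graphical exploration of concentrations at Visits 4, 6 and 7/ET against key safety and efficacy measures. SAP Sections 2 and 17 say that the SAP prevails where the two differ, so the optional wording governs.

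**The concern.** An analysis that serves a stated objective should not depend on how the other results turned out. Under this wording, someone who has seen the unblinded efficacy results may decide whether exposure against dyskinesia is summarised and plotted or left in listings. If efficacy looks good, a supportive exposure plot can be added. If it looks poor, the plot can be left out. The reader of the report could not tell a planned display from a chosen one.

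Two features of this trial make that more than a formality. First, the dose rationale in Protocol Section 1.2.1.1 is built on exposure: the lower effective macaque dose is matched to 90 mg BID in humans by Cmax, 1487 against 1480 ng/mL. Concentrations in these patients bear directly on that premise, and on whether a null result reflects lack of effect or low exposure. Second, SAP Section 9.4 drops multiplicity adjustment and says that efficacy will be weighed on all the information together. If exposure-response joins that body of evidence only when it is wanted, the weighing is tilted.

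**Working it through.** The plan gives no figure of its own on this point. The check is a comparison of passages, a comparison of visit schedules, and a rough scale.

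**1. What the analysis depends on.**

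| Source | Status of PK analysis | Condition |
|---|---|---|
| Protocol 7.9.3 | will be done | none |
| SAP 5.3 | optional | outcome of other analyses; availability of PK data |
| SAP 16, PK analyses | after lock and unblinding | judged necessary; little data leads to listings |
| SAP 16, exposure plot | optional | visits with both PK and primary efficacy assessments |

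Of the two conditions in SAP 5.3, availability can be judged by counting samples per visit, without treatment codes or results. The outcome of other analyses cannot be judged without looking at results. Neither section gives a sample threshold or says what would make the analyses necessary.

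**2. Which visits can supply an exposure plot.**

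- PK visits. Protocol Table 4, footnote bb: "Pharmacokinetic sampling will be performed at Visit 4, Visit 6, and Visit 7/ET". Protocol 6.9 agrees. Set {4, 6, 7}.
- Primary time points (SAP 6.1): {3, 5}.
- Visits at which the UDysRS sum of Parts 1, 3 and 4 enters the primary model (SAP 14.1): {3, 4, 5, 6, 7}.

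{4, 6, 7} ∩ {3, 5} = empty. {4, 6, 7} ∩ {3, 4, 5, 6, 7} = {4, 6, 7}.

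So under version 2.0 no PK sample is scheduled at a primary time point, but three visits have both a concentration and a UDysRS score. They are the three visits that Protocol 7.9.3 names for these plots.

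**3. How many displays are open to choice.** 3 visits × 2 samples (before and 1 to 2 hours after the dose) × 2 analytes × 2 outcome forms (value and change from baseline) = 24 possible plots, besides the concentration summaries.

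**4. How much the plots could show.** SAP 9.3 says that the trial stopped before 30 subjects were enrolled. With at most 29 allocated 1:1:1, about 29 × 2/3 ≈ 19 would be on active drug. I assume 10 to 20 active subjects with PK data; the documents do not give the number. The correlation detectable with 80% power at two-sided 0.05 is r = tanh[(1.960 + 0.842)/√(n − 3)]:

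- n = 10: tanh(2.802/2.646) = 0.79
- n = 15: tanh(2.802/3.464) = 0.67
- n = 20: tanh(2.802/4.123) = 0.59

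Only a strong relation would show clearly. That supports a rule on sample count. It does not support consulting the results first.

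**The case against.** The best defence is that this is a data-sufficiency rule, loosely worded. SAP 5.3 names availability of PK data as well, and the fallback sentence in SAP 16 refers to there being little to analyse. In a trial stopped this early, such a condition is ordinary. The objective is exploratory, p-values are mainly descriptive (SAP 9.4), and no inference rests on PK. All of this stands, and it limits the weight of the point. It does not remove it, because SAP 5.3 lists the outcome of other analyses as a condition separate from availability.

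A reader might go further in three ways that the documents do not support.

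- *No visit qualifies for the exposure plot, because the primary endpoint sits at Visits 3 and 5.* SAP 16 speaks of the change from baseline in the primary endpoint. That makes sense only if the endpoint there means the UDysRS sum score, which is modelled at Visits 3 to 7. Visits 4, 6 and 7 therefore qualify.
- *The visit mismatch leaves the objective unanswered.* The objective names no visit, and same-visit data exist at three. The gap at Visits 3 and 5 also concerns scheduled samples under version 2.0 only. PK is due at early termination, and SAP Section 9 assigns ET assessments to the closest scheduled visit when data there are missing, so a few samples could fall at Visit 3 or 5. For version 1.1, the design figure in SAP 4.1 is not legible enough to place its first PK entry, so that schedule is unconfirmed.
- *Skipping the analysis destroys the evidence.* SAP Sections 9 and 16 keep concentrations in listings. What can be lost is the summary and the plots.

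**Conclusion.** The concern holds for the decision rule. SAP Sections 5.3 and 16 turn an unconditional protocol analysis, serving two retained objectives, into one that can be run or reduced to listings after unblinding in the light of other results. That permits selective reporting of the exposure-dyskinesia objective. Availability of data is a proper condition; the outcome of other analyses and an undefined necessity test are not.

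The consequence is moderate. It touches the concentration summaries and up to 24 exploratory plots, and no primary efficacy estimate. It should be corrected before unblinding. The visit schedule is a matter for clear labelling, not a second defect: the plots are feasible at Visits 4, 6 and 7/ET, and they will not show exposure at the primary time points except through any reassigned ET samples.

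The conclusion rests on the SAP text as it stands and on its precedence over the protocol. The scale in the working rests on an assumed 10 to 20 active subjects with PK data. Nothing in the documents shows that selective reporting was intended.

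**What to change.** - **SAP 5.3:** strike the reference to the outcome of other analyses and keep availability of PK data as the only condition.
- **SAP 16:** strike the necessity clause. State that concentrations will be summarised by visit and time point, and that exposure-UDysRS plots will be produced, subject only to a minimum number of samples fixed before unblinding. Below that number, give listings.
- **SAP 16:** name Visits 4, 6 and 7/ET, as in Protocol 7.9.3, for same-visit plots of concentration against the UDysRS sum of Parts 1, 3 and 4. Add that under version 2.0 no PK sample is scheduled at primary Visits 3 and 5.

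SAP Section 2 says that the plan is being finalised before lock and unblinding, so the change costs some wording and a few descriptive tables and plots. The downside is that, with fewer than 30 subjects, some displays will be sparse and imprecise and should be labelled so.
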